Latin American Registry of Cardiogenic Shock in the context of Acute Coronary Syndromes (LATIN-Shock)

Investigation area Argentine Society of Cardiology

Index

Introduction	3
Objetives	3
Methods	3
Study design	
Inclusion criteria	
Exclusion criteria	
Information gathering	
Statistic analysis	
Ethical considerations	
Study organization	
Publications	
Bibliography	

Introduction:

Cardiogenic shock is a rare disease, but it constitutes the main cause of mortality in patients hospitalized for acute myocardial infarction. Its incidence ranges between 7 and 10% of infarction cases ¹ and it is associated with a mortality of 40-50% despite revascularization and the use of intra-Aortic Balloon Contrapulsation ²⁻³⁻⁴.

Most of the bibliography on this topic is North American, it is already many years old ⁵⁻⁶ and the one that is currently published mainly shows the results of different ventricular supports that are not commonly used in our environment ⁷. So far there is no record that reports the reality of Latin America. Only in Argentina, has carried out a national registry of cardiogenic shock in the context of acute coronary syndromes but have already spent more than 5 years since its publication⁸. In recent years have even changed management guidelines this pathology ⁹⁻¹⁰ and works have been published that could have changed previous behaviors ¹¹.

This is a project of the Argentine Society of Cardiology to collect epidemiological data and current management of cardiogenic shock in Latin America.

Objetives:

- 1- Determine the clinical characteristics of patients who are admitted to the coronary unit with acute coronary symptoms and present Cardiogenic Shock, either from admission or during their in-hospital evolution.
- 2- Analyze the treatment of patients with cardiogenic shock.
- 3- Observe the clinical in-hospital evolution.
- 4- Evaluates predictors of in-hospital mortality.
- 5- Compare the clinic, management and evolution characteristics in the different participating Latin American countries.

Methods:

Study design:

It is an international, multicenter, observational, prospective and consecutive registry of patients with cardiogenic shock in the context of acute coronary syndromes, which will have a duration of 12 months starting on October 1, 2021. Coronary units from different Latin American countries will be invited to participate in the registry through the different cardiology societies. Each country and each participating center will be assigned a number and patients will be included in the registry in sequential order by center (1-2-3-etc) to maintain the confidentiality of the data. Since patient data will be extracted from medical records, records will be anonymous and there will be no follow-up, informed

consent will not be required. The names of the participating centers in the different countries will appear in a list at the end of the publications, under the collective name of "LATIN Shock group".

Definition of cardiogenic shock (classic): Presence of systolic blood pressure ≤90 mm Hg for 30 minutes or requirement of vasopressors, inotropics and / or ventricular supports to maintain a blood pressure ≥90 mmHg, associated with signs of hypoperfusion and pulmonary congestion, in the absence of hypovolemia or arrhythmias that justify the clinical picture.

A new definition of cardiogenic shock has recently been proposed, which includes 5 categories¹²:

- A- At risk: Patient who does not present signs or symptoms of cardiogenic shock but is at risk of presenting it. Includes acute myocardial infarction, previous infarction, decompensated acute or chronic heart failure.
- B- Pre-shock: It is defined when there is tachycardia or hypotension without hypoperfusion. These patients must be closely monitored and carefully treated to avoid the development of classic cardiogenic shock.
- C- Classic: Patient with hypoperfusion requiring intervention (inotropics, vasopressors, or mechanical support) despite fluid resuscitation to restore perfusion.
- D- Worse: Patient similar to category C but worsening and unresponsive to initial interventions.
- E- Extreme: Includes cases where the futility of the treatment is evaluated and palliative treatment should be considered. In turn, all these categories are discriminated according to whether or not they have suffered cardiac arrest.

In this work, patients with cardiogenic shock C, D and E will be considered as a group. It will be recorded if they have presented cardiac arrest.

Inclusion criteria:

Patients of both sexes and older than 18 years, admitted to a coronary or polyvalent critical care unit, for an acute coronary syndrome with or without ST-segment elevation who present with cardiogenic shock from admission or develop it during hospitalization and who can be followed up in its evolution until hospital discharge

Exclusion criteria:

Non-ischemic cardiogenic shock (chronic heart failure, myocarditis, sepsis, tachycardiomyopathy, Takotsubo, etc.). Cardiogenic shock A and B of the new SCAI classification.

Information gathering:

The following variables will be analyzed: age, sex, risk factors and comorbidities, previous treatment, characteristics of the AMI that generated the shock, location of the infarction, Killip and Kimball on admission and evolution, time of evolution on admission, reperfusion strategies (fibrinolysis or angioplasty), if angioplasty was required: what type (primary, rescue, delayed), number of vessels operated, drug treatment instituted, hemodynamic monitoring and mechanical support (balloon pump, ECMO, mechanical ventilation, others).

The in-hospital evolution and eventual complications (fever, sepsis, COVID 19, multiorgan failure, arrhythmias, reinfarction, post-infarction angina, mechanical complications, transfusion requirement, major and minor bleeding) will be studied. Laboratory data will be collected upon admission and at 24 hours. Hemodynamic measurements will be recorded at the time of Swan Ganz catheter placement and at 24 hours (if used) and echocardiogram data. The follow-up will only be in-hospital.

The data will be collected by the researchers from the different participating centers through an electronic file developed ad hoc in Red Cap and the data will be analyzed by the executive committee that will be made up of members of the research area of the Argentine Society of Cardiology.

The Red Cap platform is a secure web application for online data management. The data will be stored securely on a server at the Argentine Society of Cardiology. For centers without Internet access, it is possible to collect data offline through Red Cap using the Red Cap mobile application that is downloaded to a tablet or mobile device. With the app, data can be collected offline and then synced with Red Cap's server. While Attachment 1 can also be printed and used to collect data for subsequent electronic submission, direct collection of electronic data is preferable to avoid transcription errors.

As it is a study that involves different countries, the data will be analyzed globally and by country initially. Different sub-studies may be carried out with the information obtained. Each participating country has the right to submit ideas for conducting sub-studies. In that case, they must be formally presented to the Executive Committee, who will carry out the analysis and provide the data if the proposal is accepted. The sub-studies should be re-evaluated by the ethics committee.

Each participating Scientific Society will receive an Excel with the data of their country once the study is finished (anonymized data) that they can present at conferences or for publication as national experiences. Each participating center

will have available immediately statistical reports (automatically generated) of the patients who have entered their center.

File in Red Cap: http://redcap.sac.org.ar/redcap/surveys/?s=RMCAYAXMF3

Statistic analysis:

The information obtained will be incorporated into a database that will be analyzed using the statistical programs Epi-info and / or IBM SPSS. For each of the observed variables, a frequency table will be constructed.

Continuous variables will be expressed as mean and standard deviation for those with a normal or Gaussian distribution and as a median with an interquartile range 25% -75% for those without such distribution. The comparison between these variables will be carried out using the Student's t test or the Wilcoxon ranksum test, as appropriate.

Discrete variables will be expressed as percentages. Statistical comparisons between them will be made using the chi-square test with Yates correction or Fisher's exact test, as appropriate.

Contingency tables will be constructed to analyze the association or independence of the variables. The analysis of the existence of associations and / or independent predictions between the different variables involved and the end points will be carried out by means of linear regression analysis and / or multiple logistic. The variables of univariate statistical significance will be entered for evaluation in the different regression models. The value corresponding to each covariate of the aforementioned analysis will be expressed as adjusted Odds Ratio and its corresponding 95% confidence interval. All statistical comparisons will be two-tailed, and p values <0.05 will be considered statistically significant.

Consent of the patient

LATIN-Shock, as an observational study, only requires data that has already been collected and is available in the patient's medical record. It does not require sensitive data. It does not involve specific interventions and there is no follow-up after discharge, therefore, informed consent is not required. However, this could be adjusted according to local regulations of the participating countries.

Ethical considerations

The protocol and the registration form will be submitted for approval by the ethics committee of the Sociedad Argentina de Cardiología, [name]. The study will be carried out in accordance with national and international ethical standards (CABA Law No. 3301, Declaration of Helsinki, and others).

As it is a descriptive study in which the data will be those normally collected in this pathology and there will be no identification of the patient or out-of-hospital follow-up, the signing of informed consent will not be required.

Study organization:

Executive committee:

Directors: [name] - [name]

Scientific and organizational secretariat: It is responsible for the organization of research, control, management and preparation of data analysis reports. It will be made up of: [name], [name], [name].

Each participating Latin American Society of Cardiology will be represented by one / two members (designated by its president) and they will be the ones who appear in the final document and receive the database of their country at the end of the study.

Collaborators: This is the name given to the members of the centers where the inclusion of the participants takes place. The head of each center where the investigation is carried out and another doctor designated by him will be specially invited, who will be in charge of preparing the registration forms.

Participating Centers:

Other Spanish-speaking Latin American Cardiology Societies will be invited to participate and they will designate the coronary units where the registry will be carried out.

Sample: It is estimated to include approximately 500 patients in one year.

Publications

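### Objective 5 compares in-hospital evolution between countries, but no case-mix-adjusted comparison is specified and country is not a named term in the planned regression

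*Combined protocol and SAP*

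**What the plan says.** Objective 5 (Objetives section) is to "Compare the clinic, management and evolution characteristics in the different participating Latin American countries". Objective 4 reads "Evaluates predictors of in-hospital mortality". The Information gathering section adds that "the data will be analyzed globally and by country initially".

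The Statistic analysis section gives these methods:

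- Continuous variables: "The comparison between these variables will be carried out using the Student's t test or the Wilcoxon ranksum test, as appropriate".
- Discrete variables: "Statistical comparisons between them will be made using the chi-square test with Yates correction or Fisher's exact test, as appropriate".
- Regression: the analysis of "independent predictions between the different variables involved and the end points will be carried out by means of linear regression analysis and / or multiple logistic". Results "will be expressed as adjusted Odds Ratio and its corresponding 95% confidence interval".
- Entry to the models: "The variables of univariate statistical significance will be entered for evaluation in the different regression models".

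The regression is not tied to a numbered objective. Country is neither named as a term nor excluded, and no adjustment set is listed for a between-country comparison.

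**The concern.** Evolution covers in-hospital complications and, read with objective 4, in-hospital death. These depend on who is admitted: age, comorbidity, infarct type, delay and severity on arrival. The same objective also compares clinical characteristics across countries, so differing case mix is a possibility the plan itself sets out to examine.

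If mortality is then compared by a chi-square or Fisher test, the result cannot separate older or sicker patients from a different outcome in comparable patients. The error can go either way: case mix can create a crude gap, or it can cancel a real one. The second case matters here because a variable that is not significant in the crude test does not reach the regression.

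The Information gathering section also gives each national society its own data for presentation or publication, so crude national figures may end up being set side by side.

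**Working it through.** **No plan figure to reproduce.** The sample of about 500 (Study organization) is an accrual estimate with no effect size, power or precision target, so nothing can be recomputed from it. The calculations below are illustrations.

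**Inputs from the documents.** About 500 patients; mortality 40-50% (Introduction); two-sided 0.05; Yates-corrected chi-square or Fisher test. The documents give neither the number of countries nor the split of patients among them.

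**Step 1: arithmetic with one risk factor.** Assume two countries with identical mortality within each stratum: 40% without the factor, and an odds ratio (OR) of 3 for the factor.

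- Odds without the factor: 0.40/0.60 = 0.667. With it: 0.667 × 3 = 2.0, so mortality is 2.0/3.0 = 66.7%.
- Country A, prevalence 20%: 0.8 × 0.40 + 0.2 × 0.667 = 45.3%.
- Country B, prevalence 40%: 0.6 × 0.40 + 0.4 × 0.667 = 50.7%.
- Crude OR: (0.507/0.493)/(0.453/0.547) = 1.24. The true country OR is 1.00.

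By a normal approximation (uncorrected test, one direction), this gap is significant in about 22% of samples with 250 per country and 11% with 100. Over factor ORs of 1.5, 2 and 3, and prevalences of 20% against 30%, 40% or 50%, the spurious gap runs from about 1 to 8 points. It is then significant in about 4-43% of samples at 250 per country, and 4-20% at 100.

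**Step 2: simulation with two covariates and no country effect.** Model: logit(mortality) = a + ln(1.5) × age/10 + ln(2.0) × arrest, with age SD 11 and a set so that overall mortality is about 45%. The effects, the SD and the imbalances are all assumed.

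| Assumed imbalance | Crude gap | Patients per country | Crude Yates test rejects | Adjusted country term rejects |
|---|---|---|---|---|
| Mean age 61 vs 69; arrest 15% vs 35% | about 10.8 points | 250 | 65% | about 4-5% |
| Same | same | 100 | 31% | about 4-5% |
| Mean age 63 vs 67; arrest 20% vs 30% | about 5.4 points | 250 | 19% | about 4-5% |
| Same | same | 100 | 9% | about 4-5% |

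The return to about 5% is built in, because the model adjusts for exactly the two variables that generated the deaths. Real adjustment would be less complete.

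**Step 3: the plan's screening rule, if country counts as a candidate variable.** Country enters only when its crude test is significant.

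- No true effect: country is significant in the final model in 2.5% and 4.1% of runs (large imbalance, 250 and 100 per country) and in 2.8% and 2.9% (mild imbalance). The rule then removes the spurious finding from the adjusted result.
- True country OR of 0.6, masked by the large imbalance, 250 per country: the rule finds it in 2.5% of runs, against 71% when country is forced in.

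**Step 4: feasibility.** Expected deaths are 500 × 0.40 = 200 to 500 × 0.50 = 250. That supports country plus a moderate fixed set of covariates if countries are few. A country number is assigned (Study design), and age, sex, comorbidities, infarct location, Killip class on admission and time of evolution are collected (Information gathering). Cardiac arrest is recorded (Study design), but its timing is not stated.

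**The case against.** A reader might infer that only crude tests are planned. The documents do not support that: regression with adjusted odds ratios is planned, is not confined to any objective, and could include country. If country is a candidate, a spurious crude difference triggers its entry and is mostly adjusted away (step 3). This stands as far as it goes. But it depends on a choice the plan leaves unstated, and it does nothing for a difference that case mix hides.

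A reader might also infer that crude gaps will be reported as country effects, or that country mortality is the main output. No passage says either. The comparison is part of the last of five objectives, and the Ethical considerations section calls the study descriptive. For clinical characteristics, and largely for management, unadjusted figures by country are the intended result.

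The percentages in step 2 describe a crude test taken alone under assumed effects and two equal countries. They show that the problem can be material, not how large it will be in this registry.

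Finally, forcing a long covariate list into every complication model would be costly. At an assumed 5% event rate, 500 patients give only 25 events. That limits the fix to mortality and to complications with enough events.

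**Conclusion.** The point holds for in-hospital evolution, chiefly mortality. By default the between-country comparison is unadjusted. The planned regression neither names country nor fixes a case-mix set, and its entry rule can lose a masked country difference. This is more than a missing detail, because a better method is available from data already collected.

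The size rests on assumptions outside the documents: false rejection by the crude Yates test of about 9-65% against about 5% adjusted, and detection of a masked OR of 0.6 in 2.5% of runs against 71%. The direction of the bias, and whether it matters in this registry, cannot be known in advance. The change should be made before the country data are analysed.

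**What to change.** Add to the Statistic analysis section:

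> The between-country comparison of in-hospital mortality will use a logistic model with country forced in and a fixed set of admission covariates entered whatever their p-value: age, sex, ST-elevation or not, infarct location, Killip class on admission, time of evolution on admission, main comorbidities, and cardiac arrest if its timing shows it was present at admission. The model will allow for clustering by centre. Case-mix-standardised mortality by country will be shown beside the crude figure. Crude by-country outcome tables, including those for complications, are descriptive only.

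The main comorbidities should be listed by name before the data are examined. If the form does not record when arrest occurred, either add that item or leave arrest out of the set.

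Cost: SAP wording, one more model and some degrees of freedom. Countries with few patients may need pooling, by a rule set in advance. Complications should be modelled only where there are enough events.

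### If a Swan-Ganz value passes the univariate entry rule, the mortality model can be restricted to catheterised patients, whose number the plan does not state

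*Combined protocol and SAP*

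**What the plan says.** The fourth item under Objetives is "Evaluates predictors of in-hospital mortality". Study design describes a prospective registry of consecutive patients.

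On data, Information gathering says "Hemodynamic measurements will be recorded at the time of Swan Ganz catheter placement and at 24 hours (if used". The same section collects laboratory values on admission and at 24 hours. Under Consent of the patient, the registry is limited to what the medical record already holds, so a catheter value that was never measured cannot be obtained later.

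On analysis, the Statistic analysis section covers "The analysis of the existence of associations and / or independent predictions between the different variables involved and the end points", which "will be carried out by means of linear regression analysis and / or multiple logistic". The entry rule is "The variables of univariate statistical significance will be entered for evaluation in the different regression models". The threshold is "All statistical comparisons will be two-tailed, and p values <0.05 will be considered statistically significant". The section names no candidate predictors, sets no completeness limit, makes no exception for variables measured only in some patients, and gives no method for missing data.

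**The concern.** The entry rule looks only at the p-value. It takes no account of how many patients have the variable, or why the others lack it. Swan-Ganz values are absent by design in anyone who did not have the catheter, and catheter placement is a clinical decision that is likely to vary between centres.

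A logistic model, as usually fitted, uses only patients with every covariate present. One catheter value in the model can therefore remove all uncatheterised patients. This affects more than the catheter term: the adjusted odds ratios for age, infarct location, reperfusion and every other covariate would then be estimated in the catheterised group alone. A reader would take them as predictors for the whole registry.

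The 24-hour readings raise a separate issue. A patient who dies before the reading cannot have it, whether it comes from the catheter or the laboratory. Entering such a value drops early deaths from a model whose outcome is death.

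**Working it through.** **Inputs from the documents.** Registry size: "It is estimated to include approximately 500 patients in one year" (Sample, under Study organization). Background mortality: "it is associated with a mortality of 40-50% despite revascularization" (Introduction). Two-sided significance level 0.05 (Statistic analysis). The 500 is an accrual estimate with no power or precision calculation behind it, so there is no stated calculation to reproduce.

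**Input that is assumed.** The share of patients catheterised, u. The documents do not give it, so a wide range is shown.

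**Full registry.** Deaths = 500 × 0.40 to 500 × 0.50 = 200 to 250, before any other missing data.

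**Model containing a catheter value, incomplete records dropped.**
- Patients: n = 500 × u.
- Deaths: n × 0.40 to n × 0.50. This gives catheterised patients the background mortality. They are a selected group, so their true figure may differ.
- Standard-error ratio: √(500/n) = 1/√u, assuming similar mortality and covariate spread in the subset.
- Power: for an illustrative two-level predictor that splits patients equally, with 40% against 55% mortality, two-sided 0.05. With all 500 patients it is 92%.

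| Assumed u | Patients | Deaths | Standard-error ratio | Power |
|---|---|---|---|---|
| 10% | 50 | 20–25 | 1/√0.10 = 3.16 | 18% |
| 30% | 150 | 60–75 | 1/√0.30 = 1.83 | 45% |
| 50% | 250 | 100–125 | 1/√0.50 = 1.41 | 66% |
| 90% | 450 | 180–225 | 1/√0.90 = 1.05 | 89% |

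**Chance that a catheter value enters.** The univariate test of a catheter value is itself run only in catheterised patients. For a value split at its median with the same 40% against 55% contrast, the power column is also the chance of passing the entry rule. Where the loss would be largest (u = 10%), one such value passes about 18% of the time. Where the loss would be slight (u = 90%), it passes about 89% of the time. Several values at two time points are open to testing, so the chance that at least one enters is higher than for a single value.

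**24-hour readings.** No size can be computed. The documents do not give the share of patients who die before 24 hours, and they do not say whether the catheter clock runs from admission or from placement. The direction is clear: deaths before the reading are lost from the model and later deaths are not.

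**The case against.** The best reply is that the plan permits this outcome but does not require it. Significant variables go forward for evaluation in several models, and nothing says that one model must hold them all. Information gathering lists hemodynamic monitoring among the variables to be analysed but mentions the catheter measurements in a separate sentence, as data to be recorded. A sensible analyst could keep them apart. A catheter value must also reach p<0.05 among catheterised patients, which is less likely when they are few. Dropping incomplete records is the usual software default; the plan does not state it. Objective 4 does not say that the predictors must hold for all shock patients. The study calls itself descriptive, and names objective 4 as one of five.

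Much of this stands, and it makes the concern conditional. A reader might infer that the plan's rule sends catheter values into the model; the text does not go that far. The gap remains, however. The scope of variables to be tested is broad, significance is the only stated filter, and nothing keeps a catheter value out. The consecutive design makes the whole registry the natural population for objective 4. The loss would be visible from the number of patients in the model, but the plan does not commit to reporting it.

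On the 24-hour values, it is fair to say that the laboratory readings are not limited to a treated subset, and that a patient whose shock develops later in the stay may have the reading before onset. The issue there is survival to the reading, which is why it is kept apart from the catheter point.

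**Conclusion.** The concern holds in conditional form. If a Swan-Ganz value is significant and is entered, and incomplete records are dropped, the objective 4 model can be restricted to catheterised patients, and all its adjusted odds ratios then describe that group.

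A reader might infer that the remaining set would be small. The documents do not support that, because they give no rate of catheter use. Across assumed use of 10% to 90%, the model keeps 50 to 450 of 500 patients. At the low end the loss of precision is severe. At the high end it is about 5%, and the remaining problem is that the population is selected.

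The conclusion rests on three conditions: a catheter value reaches p<0.05 in its own subset, it is placed in the mortality model, and the complete-case default applies. The loss of early deaths through 24-hour values is a separate weakness of unknown size, and it can arise through the laboratory data even if no catheter value is significant.

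**What to change.** Amend the entry rule in Statistic analysis:

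- Swan-Ganz values are not candidates for the main mortality model. Report them descriptively, or in a labelled secondary model limited to catheterised patients.
- Use 24-hour values, catheter or laboratory, only in a labelled secondary analysis of patients alive at that reading.
- For every model, report the number of patients and the number of deaths used.

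The cost is a few sentences in the plan and a separate secondary analysis; no new data are needed. The downside is that invasive hemodynamics could not be called independent predictors of mortality for the whole registry. The data could not support that claim in any case, since uncatheterised patients have no values.

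### The pooled model for predictors of in-hospital mortality does not commit to a country term, so its odds ratios may mix within-country and between-country associations

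*Combined protocol and SAP*

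**What the plan says.** All references are to the combined protocol and SAP.

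- **Objectives.** Objective 4: "Evaluates predictors of in-hospital mortality". Objective 5: "Compare the clinic, management and evolution characteristics in the different participating Latin American countries".
- **Study design.** Each country and each centre receives a number, so country is known for every patient.
- **Information gathering.** The list of variables to be analysed includes time of evolution, reperfusion strategy, type of angioplasty, drug treatment, monitoring and mechanical support. Country is not on it. The level of analysis is given later in that section: "As it is a study that involves different countries, the data will be analyzed globally and by country initially".
- **Statistic analysis.** The search for "independent predictions between the different variables involved and the end points" "will be carried out by means of linear regression analysis and / or multiple logistic". Variables significant in univariate testing are entered, and results are adjusted odds ratios with 95% confidence intervals. No covariate is forced in, and no term, stratum or random effect for country is named.
- **Sample line, under Participating Centers.** "It is estimated to include approximately 500 patients in one year". The number of countries and the patients expected from each are not given.

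**The concern.** Country confounds a predictor of death when two things hold: mortality differs between countries, and so does the frequency of the predictor. Objective 5 makes both a subject of study. Angioplasty, balloon pump use and delay are plausible examples of factors whose frequency depends on where the patient was treated.

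If the pooled model leaves country out, such a factor takes on part of the mortality level of the countries that use it most. It may then be reported as an independent predictor although it has no association with death inside any country. A real association may equally be weakened. Readers will take the adjusted odds ratios as statements about patients and treatments, so it matters whether they partly describe geography.

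**Working it through.** **Inputs from the documents.** About 500 patients. Mortality from the Introduction: "it is associated with a mortality of 40-50% despite revascularization". Two-sided alpha 0.05. The figure of 500 is an enrolment estimate with no effect size, power or precision target, so there is no sample-size calculation to reproduce.

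**Inputs assumed.** Number of countries, their sizes, and how far mortality and factor use differ between them.

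**Step 1. Deaths.** 500 × 0.40 = 200 and 500 × 0.50 = 250.

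**Step 2. The mechanism, with a strong assumed contrast.** Two country blocks of 250. Angioplasty 80% in A and 40% in B; mortality 35% in A and 55% in B; no effect of angioplasty within either block.

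- With angioplasty: 200 × 0.35 + 100 × 0.55 = 70 + 55 = 125 deaths in 300.
- Without: 50 × 0.35 + 150 × 0.55 = 17.5 + 82.5 = 100 deaths in 200.
- Pooled OR = (125/175) / (100/100) = 0.714, against a true within-country OR of 1.
- SE of log OR = √(1/125 + 1/175 + 1/100 + 1/100) = 0.184, so the 95% CI is 0.50 to 1.02.
- z = 0.336/0.184 = 1.83, and the chance of p<0.05 is about 45% (41% with the Yates correction that the plan names).

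**Step 3. The same calculation with other assumed contrasts.** Two equal blocks, true within-country OR of 1:

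| Mortality | Factor use | Pooled OR without country |
|---|---|---|
| 40% vs 50% | 50% vs 50% | 1.00 |
| 40% vs 50% | 40% vs 60% | 1.08 |
| 40% vs 50% | 30% vs 70% | 1.18 |
| 30% vs 60% | 30% vs 70% | 1.63 |

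Second row as a check: 115/250 against 110/250 deaths gives (115/135)/(110/140) = 1.08. With equal factor use there is no bias.

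**Step 4. False-positive rate for one null factor.** Simulation of 500 patients in eight assumed countries (180, 90, 70, 50, 40, 30, 25, 15), 3,000 runs per setting. Country effects are normal on the logit scale. To read the SDs: around 45% mortality (logit −0.2), SD 0.3 puts about two thirds of countries between 38% and 52%, and SD 0.5 between 33% and 57%. Around 50% factor use, SD 0.5 gives 38% to 62% and SD 1.0 gives 27% to 73%.

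| SD mortality | SD factor | p<0.05 without country |
|---|---|---|
| 0.3 | 0.5 | 6.5% |
| 0.5 | 0.5 | 7.1% |
| 0.3 | 1.0 | 8.1% |
| 0.5 | 1.0 | 11.9% |

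Stratified by country, the rate was 5.1-5.6% throughout. A separate simulation with ten equal countries (800 runs per setting, logistic model) gave 4.9% with no country variation, with or without the country term. For SDs 0.3/0.5, 0.5/0.5 and 0.5/1.0 it gave 5.6%, 6.8% and 12.4% without country, and 4.8%, 4.3% and 6.3% with it. A more extreme setting did not complete and is not used. These models hold one factor; the other covariates in the plan's model could absorb part of the country effect.

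**Step 5. What the country term uses up.** At an assumed yardstick of ten deaths per parameter, 200-250 deaths support about 20-25 parameters. Ten countries take 9 and leave about 11-16.

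**Step 6. Deaths per country under an equal split.** 200-250 deaths over 2 countries is 100-125 each, over 5 it is 40-50, and over 10 it is 20-25. If one of ten countries supplies half the patients, it has 100-125 deaths and each of the others about 11-14 (100/9 to 125/9).

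**The case against.** **Country is not excluded.** It is recorded, and the screening rule would admit it if the analysts treated it as a candidate and it reached significance. This matters most in the Step 2 example, where 35% against 55% mortality gives a Yates chi-square of 19.4. Country would pass the screen in 99.6% of simulated registries, and the null factor would then survive both its univariate screen and the stratified test in 2.3%, not 45%. In the eight-country layout the same rule retains the null factor in 2.8-4.1% of runs. So the error rates in Step 4 apply only if country is left out of the candidates. That stands. But country is not on the variable list, so its candidacy is a guess. Even as a candidate it reached significance in only about 47% of runs at mortality SD 0.3 (84% at SD 0.5). Adjustment for a known possible confounder should not depend on that test.

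**The sizes are assumed.** This also stands. No document figure describes variation between countries. With modest variation the excess is one or two percentage points, and pooled odds ratios of 1.08-1.18 are small biases.

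**By country may mean descriptive only.** A reader might infer that the mortality model is to be refitted in each country, with unstable odds ratios from few deaths. The documents do not support that as fact. The sentence on global and by-country analysis speaks of the data in general and stands under Information gathering. The regression text mentions no country-level models, and Objective 5 can be met with descriptive comparisons. Nor would deaths necessarily be few: two countries, or one dominant country, could have 100 or more.

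**Conclusion.** The concern holds for the pooled model. The plan leaves open whether country enters the mortality regression, while its own objectives allow that country is related to both treatment and outcome. If country is omitted, a null factor is declared significant in about 6-12% of analyses instead of about 5%, under assumed variation across eight countries. The upper end needs large differences in factor use. With modest variation the bias is small, and with none it is absent.

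Two stronger readings go beyond the text. One is that the plan rules out a country term: it is silent and does not prohibit one. The other is that the plan fits separate predictor models in each country: it does not say so. The second leaves only a need for clarification, since the number of countries and the split of patients are not stated. The point is worth correcting because the fix costs almost nothing, not because serious bias has been shown.

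**What to change.** Add to Statistic analysis: *The pooled logistic model for in-hospital mortality will include country, as a fixed stratum or a random intercept, whatever its univariate p-value.*

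Add a clarification to the sentence on global and by-country analysis: *By-country results are descriptive*, or, if national models are wanted, *any country-level regression is exploratory, given the number of deaths likely in a single country*.

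The cost is SAP wording and a few degrees of freedom, one fewer than the number of countries if the term is fixed. No new data are needed, because the country number is already collected. National societies keep their data and their right to publish.
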